4.2.1 Required medications

- If HIV positive, participants must be on stable antiretroviral therapy for a minimum of 12 weeks prior to study enrollment. Antiretroviral therapy with a minimum of three active drugs, which may include the HIV protease inhibitors, non-nucleoside reverse transcriptase inhibitors (NNRTI), nucleoside (and nucleotide) reverse transcriptase inhibitors (NRTI), integrase strand transfer inhibitors (INSTI), CCR5 antagonists, or fusion inhibitors, is strongly recommended.
- If HIV positive, chemoprophylaxis for *Pneumocystis jirovecii* pneumonia is required for all participants with a CD4 count ≤ 200 cells/mm³.
- Participants refusing antiretroviral therapy for HIV are ineligible to participate in this study.

4.2.2 Permitted medications

- Topical and/or antifungal agents are permitted for prophylaxis.
- Treatment maintenance or chemoprophylaxis with approved agents for opportunistic infections as clinically indicated is permitted.
- Regularly prescribed prescriptions such as antipyretics, analgesics, allergy medications, anti-depressants, sleep medications, oral contraceptives, megestrol acetate, testosterone, or any other medications which are not specifically prohibited will be allowed. This will include alternative therapies such as vitamins, acupuncture, and visualization techniques. Participants should, however, report the use of these therapies, and they will be recorded. However, aspirin or NSAIDS will not be permitted.
- Low dose prophylactic heparin will be permitted.

4.2.3 Prohibited medications

- Investigational drugs will be prohibited as will systemic cytotoxic chemotherapy or other KS-specific treatments.

4.3 Duration of Therapy

In the absence of treatment delays due to AE(s), treatment may continue for a maximum of 12 cycles or until one of the following criteria listed in [Section 4.5](#) applies. If CR is achieved, the participant will receive one cycle beyond CR. Treatment may be resumed if KS progresses off treatment after a CR, up to a maximum of 12 cycles. The participant will resume the previous dose that he/she was receiving when CR was achieved. Participants who achieve PR or SD may continue the treatment at the dose he/she was receiving when PR or SD was achieved for a maximum of 12 cycles, if the participant and treating physician feel that it is beneficial to continue treatment.

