4.5 Criteria for Removal from Treatment

Participants will be removed from study treatment when any of the criteria listed in [Section 5.0](#) and below applies. The reason for study treatment removal and the date of the participant's last treatment must be documented in the Off Protocol Treatment Form in Advantage eClinical. The date the participant was removed from study treatment must be documented in the source.

- Uncontrolled sustained hypertension, which will be defined as systolic BP > 140, and diastolic BP > 90, even with use of antihypertensive medications.
- Disease progression after completing 2 or more cycles (or at least after 4 doses of sEphB4-HSA).
- Dose delay of more than 28 days.
- Rapid progression of disease that is deemed to be life-threatening.
- Intercurrent illness that prevents further administration of treatment.
- Any participant who develops Multicentric Castleman's disease or a life-threatening systemic inflammatory syndrome will not receive further sEphB4-HSA and will be managed using the best judgment of the treating physician.
 - **These events require mandatory notification of a study chair within 24 hours which will result in immediate notification of all participating sites and a conference call to assess the safety of continued enrollment.**
- Participants who experience Steven-Johnson Syndrome or major allergic reaction.
- Participants who become pregnant or need to breast-feed.
- Participants who require systemic chemotherapy for the treatment of a malignancy other than KS.
- Participants who are noncompliant with respect to taking drugs, keeping appointments, or having tests required for the evaluation of drug safety and efficacy.
- Participants have the right to withdraw from the study at any time for any reason.

- The Investigator has the right to remove participants from the study for clinical reasons which he/she believes are life-threatening to the participant even if such reasons do not fall into the toxicity classifications discussed in [Section 5.0](#).
- General or specific changes in the participant's condition render the participant unacceptable for further treatment in the judgment of the investigator.
- Unacceptable AE(s).

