5.2 Dose Modifications for Non-Hematologic Toxicity (EXCEPT hypertension)

See [Section 5.4](#) for dose modifications for hypertension.

Symptomatic grade 2 toxicity

If the participant experiences a new symptomatic grade 2 non-hematologic toxicity, sEphB4-HSA will be withheld until the toxicity has resolved to \leq grade 1. sEphB4-HSA will then be resumed at the same weekly dose. If the symptomatic grade 2 toxicity recurs despite optimal supportive care (e.g., fluids, electrolyte replacement, anti-diarrheal medications), sEphB4-HSA will be withheld until the toxicity has resolved to \leq grade 1, and the weekly dose may be reduced by one dose level. If symptomatic grade 2 toxicity recurs at the reduced dose, sEphB4-HSA treatment will be discontinued.

Grade 3 or 4 toxicity

If the participant experiences grade 3/4 non-hematologic toxicity, sEphB4-HSA must be withheld until the toxicity has resolved to \leq grade 1 or baseline. sEphB4-HSA will then be resumed at a weekly dose that is reduced by one dose level. If the grade 3/4 toxicity recurs at the lower dose (level -1) dosing, sEphB4-HSA treatment will be stopped. If any participant experiences Steven-Johnson Syndrome, major allergic reaction which requires epinephrine, grade 3 neuropathy lasting at least 4 weeks, or grade 4 non-hematological toxicity that does not resolve with optimal supportive care (e.g., fluids, electrolyte replacement, anti-diarrheal medications), sEphB4-HSA must be discontinued, and the participant taken off study.

See below for a summary of dose modifications for non-hematologic toxicities.

Table 5-B: Summary of dose modifications for non-hematologic toxicity (except for hypertension)

OCCURRENCE	SYMPTOMATIC GRADE 2	GRADE 3/4
1 st	Hold until \leq grade 1, then resume at same dose	Hold until \leq grade 1 or baseline, then reduce sEphB4-HSA by one dose level
2 nd	Hold until \leq grade 1 then reduce dose by one dose level. If the dose is a lowest level, sEphB4-HSA may be stopped	Stop treatment
3 rd	Stop treatment	N/A

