In the case of grade 3 hypertension as documented by two or more different measurements - that are at least 30 minutes apart and measured by a healthcare provider - treatment with sEphB4-HSA must be held until hypertension returns to target BP (<140/90 mm Hg). Participants should be initiated on antihypertensive therapy, or if already on antihypertensive therapy, participants should have their antihypertensive therapy titrated, per the treating physician. BP should be rechecked 3-5 days after initiation or titration of antihypertensive therapy, or after approximately 5 half-lives to allow antihypertensive drug levels to achieve steady state (~5 days for an antihypertensive dosed daily and ~3 days for one dosed twice daily). If SBP is still ≥ 140 mm Hg and/or DBP is ≥ 90 mm Hg, the antihypertensive dose should be increased, or additional antihypertensive therapy added as indicated. Continue to monitor BP and titrate antihypertensives every 3-5 days until target BP (<140/90 mm Hg) is achieved. sEphB4-HSA should be held until hypertension returns to target BP (<140/90 mm Hg) and patient is asymptomatic, at which point sEphB4-HSA

[figure not shown]
treatment can be resumed.

If after subsequent dosing of sEphB4-HSA, grade 3 hypertension recurs - as documented by two or more different measurements that are at least one hour apart and measured by a healthcare provider - hold sEphB4-HSA and titrate antihypertensives as above until target BP (<140/90 mm Hg) is achieved. When subsequent dosing of sEphB4-HSA is restarted, patient will require reduction of sEphB4-HSA by one dose level.

If patient has to hold treatment for 4 weeks due to hypertension, sEphB4-HSA treatment will be discontinued.

All participants must be educated about the hypertension side effect and instructed to contact the study team if their BP remains under poor control between visits. It is recommended participants keep a BP log, but this is up to the treating physician's discretion.

Hypertension Management Schema

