5.6 Dose Interruptions

Participants who have a delay in administration of a dose of the study drug of ≤ 48 hours should take the planned dose as soon as possible after the intended time of administration and continue on the same 28-day cycle (i.e., Day 15 of the same cycle will not change if Day 1 is delayed, or the next cycle start date Day 1 will not be delayed). Relevant evaluations due prior to the next sEphB4-HSA dose may be delayed accordingly.

For participants who have a delay in administration of study drug of >48 hours but ≤ 28 days (please refer back to [Sections 5.2](#), [5.3](#), and [5.5](#) for hold and stop parameters for non-hematologic and hematologic toxicities), the study drug administration may continue with the following instructions: If the Day 1 dose of any new cycle is delayed ≥ 48 hours, that cycle start date and subsequent treatment days and cycles will be reset. If the Day 15 dose of is delayed ≥ 48 hours, the following Day 1 dose of the next cycle will not be given until 14 days later. All relevant evaluations will be delayed accordingly.

Any dose interruption of more than 28 days requires discontinuation of protocol therapy.

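### The dose for re-treatment after a complete response is not made subject to Section 5, and Sections 4.5 and 5.6 state no exception for that re-treatment

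*Combined protocol and SAP*

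**What the plan says.** **Re-treatment.** A participant who reaches CR receives one further cycle and stops. Section 4.3 then provides: "Treatment may be resumed if KS progresses off treatment after a CR, up to a maximum of 12 cycles". The dose on resumption is set in the next sentence: "The participant will resume the previous dose that he/she was receiving when CR was achieved". The dose sentence appears six times: in the synopsis, the protocol schema, and Sections 2.4, 4.1, 4.3 and 10.1. None of the six refers to toxicity after CR.

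**Dose reduction.** Section 5.2, on grade 3/4 non-hematologic toxicity once it has resolved, says: "sEphB4-HSA will then be resumed at a weekly dose that is reduced by one dose level". (The word weekly does not fit the two-weekly schedule, but this does not affect the point.) Section 5.4, on grade 3 hypertension that recurs, says: "When subsequent dosing of sEphB4-HSA is restarted, patient will require reduction of sEphB4-HSA by one dose level". Table 5-A gives the levels as 10, 7.5 and 5.0 mg/kg.

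**Removal.** Section 4.3 opens by saying that "treatment may continue for a maximum of 12 cycles or until one of the following criteria listed in" Section 4.5 applies. Section 4.5 is mandatory in form: "Participants will be removed from study treatment when any of the criteria listed in" Section 5.0 or its own list is met. That list includes "Disease progression after completing 2 or more cycles (or at least after 4 doses of sEphB4-HSA" and a dose delay of more than 28 days. Section 5.6 ends: "Any dose interruption of more than 28 days requires discontinuation of protocol therapy".

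**The concern.** The main issue is dose safety. The resume-dose rule looks back to the day CR was achieved, but one more cycle of drug is given after that day. If toxicity in that cycle calls for a lower dose, the protocol gives two doses for the same infusion and does not say which prevails. The error goes in the unsafe direction if Section 4.3 is followed. By the time of relapse the toxicity may have resolved, so nothing at the bedside would prompt the site to look back at Section 5.

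The second issue is smaller. The relapse that Section 4.3 uses as its trigger can also be progression under Section 4.5, and the time off drug can exceed 28 days. Sites in a multi-institutional trial could handle the same relapse differently, and Section 4.5 requires the reason for removal to be recorded.

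**Working it through.** **1. Dose: the rules side by side.** Take a participant in CR at 10 mg/kg who has a first grade 3 non-hematologic toxicity in the extra cycle, later relapses off treatment and is re-treated.

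| Source | Dose on re-treatment |
|---|---|
| Section 4.3, dose at CR | 10 mg/kg |
| Section 5.2 with Table 5-A, one level lower | 7.5 mg/kg |

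Ratio: 10 / 7.5 = 1.33, so 33% above the dose Section 5 requires. If the toxicity follows the Day 15 dose of the extra cycle, the first re-treatment infusion is the first dose to which the reduction could apply. If it follows the Day 1 dose and resolves in time, the Day 15 dose is already 7.5 mg/kg, and the literal Section 4.3 text would raise it again. Recurrent grade 3 hypertension under Section 5.4 gives the same result.

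Two limits apply. A reduction made before CR is already contained in the dose at CR. A first episode of grade 3 hypertension calls for a hold, not a reduction.

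**2. The discontinued dose.** Section 10.1 records 3 participants treated at 15 mg/kg, a level that Section 4.1 says has been discontinued. CR at that dose would, read literally, mean resuming at 15 / 10 = 1.5 times the current starting dose. The documents do not say that any of the 3 reached CR.

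**3. Removal: does the Section 4.5 threshold separate the two rules?** Tumor assessment is on Day 1 of each cycle (Section 9.0). For a fully dosed participant:

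- CR first seen on Cycle 2 Day 1: 2 doses, plus 2 in the extra cycle = 4 doses, or 2 cycles.
- CR counted only after the 4-week persistence in Section 9.1.1: 4 doses, plus 2 = 6 doses, or 3 cycles.

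Both reach the threshold of 2 cycles or 4 doses, so exposure does not keep the rules apart. The overlap is still incomplete. Section 2.4 speaks of KS that returns, and Section 9.1.6 defines recurrence separately from progression. With 50 or fewer lesions, and counting from a lesion-free CR, 25% of 0 is 0. The lesion-count criterion then needs 5 new lesions, and 1 to 4 would be recurrence without meeting it. Section 9.1.4 does not state the reference count, so counting from CR is an assumption.

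**4. How many participants.** The documents give no expected CR rate on this drug, no relapse rate and no rate of reductions in the extra cycle. For order of magnitude only, assume CR in 2% to 10% of 20 participants, off-treatment relapse in 25% to 75% of those, all of them re-treated, and a reduction due in 5% to 15% of those:

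- Low: 20 × 0.02 × 0.25 × 0.05 = 0.005 participants.
- High: 20 × 0.10 × 0.75 × 0.15 = 0.225 participants.

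None of these rates comes from the protocol, so this is not an estimate.

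**5. Primary decision rule (Section 10.2).** With n = 20, at least 9 responders and at most 3 unacceptable toxicities, exact binomial probabilities are:

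- P(R ≥ 9 | 0.60) = 0.9435 and P(T ≤ 3 | 0.10) = 0.8670. With response and toxicity independent, power = 0.9435 × 0.8670 = 0.818 (stated 0.82).
- P(R ≥ 9 | 0.30) = 0.1133 and P(T ≤ 3 | 0.30) = 0.1071. The larger is 0.113 (stated 0.11).

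The plan's figures reproduce. None of the inputs depends on how re-treatment is handled.

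**The case against.** The strongest reply is that an experienced site would reconcile the text without help. Section 4.1, which carries the resume-dose sentence, also refers dose modifications to Section 5.0, so the dose at CR can be read as a default. Section 4.3 uses the same construction for participants continuing in partial response or stable disease, and nobody would take that to cancel a later reduction. Section 5.4 is itself mandatory about restarting. On removal, a participant who relapses off treatment has no current treatment to be removed from. A permission given six times is the specific rule and should prevail over a general bullet. Section 5.6 deals with delayed doses, and after a planned stop no dose is due.

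Most of this stands for the removal question. A reader might infer that Section 4.5 or 5.6 forbids re-treatment after CR. The documents do not support that, because it would defeat an express and repeated permission. What remains is a missing statement of the exception.

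For the dose, the reply shows what was probably meant but not what is written. No section says that Section 5 prevails, and the dose sentence says the participant will resume the dose at CR. A reader might also infer that someone is due to return to 15 mg/kg, or that the number affected can be estimated. The documents support neither.

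**Conclusion.** The point holds as a minor one. The resume-dose sentence, taken literally, sets a dose one level above the one Section 5.2 or 5.4 requires when a reduction falls due in the cycle after CR: 10 instead of 7.5 mg/kg in the ordinary case. That is a stated rule giving an unsafe dose, and so more than missing detail. The absence of a post-CR exception in Sections 4.5 and 5.6 is a matter for clarification.

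The dose conflict needs a CR, a reduction due in one particular cycle, a relapse off treatment and a decision to re-treat, so very few participants could be affected. No reader should infer a threat to the primary result. A participant in CR is already a responder, Section 9.0 confines the primary toxicity report to the first two cycles, and the thresholds, power and significance level do not change.

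**What to change.** In Section 4.3, replace the resume-dose sentence with wording such as: *If KS recurs or progresses off treatment after a CR, treatment may be restarted, up to 12 cycles in total, at the lower of the dose at CR and the dose currently permitted by Section 5, and not above 10 mg/kg.* Carry the same text into the synopsis, the schema and Sections 2.4, 4.1 and 10.1. The cap is a precaution that could matter only for the 3 participants treated at 15 mg/kg.

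In the progression and dose-delay bullets of Section 4.5 and the last sentence of Section 5.6, add: *except the planned stop after CR and the off-treatment relapse that triggers re-treatment under 4.3*.

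The cost is one sentence, one exception clause in three places and matching text in five, all in a single amendment. It adds no visits, procedures or participants.

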4.4 Duration of Follow-up

Participants who have PR or better will be followed up every three months, for up to one year, or until an earlier time of disease progression requiring additional treatment. All other participants will be followed for 4 weeks after completion of study treatment, removal from study treatment, or until death, whichever occurs first. Participants who do not achieve a PR or better and are removed from treatment early will be reported as off-treatment on the last date of agent administration. Participants removed from study treatment for unacceptable AE(s) will be followed until resolution or stabilization of the AE. Participants who withdraw from treatment for toxicity reasons should be followed until the toxicity resolves/returns to baseline, or for 4 weeks, whichever is later. In addition, participants who go off study treatment for reasons other than toxicity should be followed for at least 4 weeks after discontinuing drug.

4.5 Criteria for Removal from Treatment

Participants will be removed from study treatment when any of the criteria listed in [Section 5.0](#) and below applies. The reason for study treatment removal and the date of the participant's last treatment must be documented in the Off Protocol Treatment Form in Advantage eClinical. The date the participant was removed from study treatment must be documented in the source.

- Uncontrolled sustained hypertension, which will be defined as systolic BP > 140, and diastolic BP > 90, even with use of antihypertensive medications.
- Disease progression after completing 2 or more cycles (or at least after 4 doses of sEphB4-HSA).
- Dose delay of more than 28 days.
- Rapid progression of disease that is deemed to be life-threatening.
- Intercurrent illness that prevents further administration of treatment.
- Any participant who develops Multicentric Castleman's disease or a life-threatening systemic inflammatory syndrome will not receive further sEphB4-HSA and will be managed using the best judgment of the treating physician.
 - **These events require mandatory notification of a study chair within 24 hours which will result in immediate notification of all participating sites and a conference call to assess the safety of continued enrollment.**
- Participants who experience Steven-Johnson Syndrome or major allergic reaction.
- Participants who become pregnant or need to breast-feed.
- Participants who require systemic chemotherapy for the treatment of a malignancy other than KS.
- Participants who are noncompliant with respect to taking drugs, keeping appointments, or having tests required for the evaluation of drug safety and efficacy.
- Participants have the right to withdraw from the study at any time for any reason.

- The Investigator has the right to remove participants from the study for clinical reasons which he/she believes are life-threatening to the participant even if such reasons do not fall into the toxicity classifications discussed in [Section 5.0](#).
- General or specific changes in the participant's condition render the participant unacceptable for further treatment in the judgment of the investigator.
- Unacceptable AE(s).

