- ___ 3.2.12 Female participants who are pregnant, lactating, or breastfeeding.
- ___ 3.2.13 Pregnant women are excluded from this study because sEphB4-HSA has not been tested in pregnant women and it could have potential teratogenic or abortifacient

effects. Because there is an unknown but potential risk for adverse events in nursing infants secondary to treatment of the mother with sEphB4-HSA, breastfeeding should be discontinued if the mother is treated with sEphB4-HSA.

- ___ 3.2.14 Participants with a recent history (< 6 months) of a major infarct including but not inclusive to bowel ischemia, cerebral vascular accident, transient ischemic attack, myocardial infarction, limb ischemia, or skin necrosis.
- ___ 3.2.15 Participants with a QTcF (Fridericia Correction Formula) > 480 ms on 2 out of 3 electrocardiograms (EKGs) (if first EKG is < 480, no need to repeat, if first EKG is > 480 repeat twice for a total of 3 EKGs).
- ___ 3.2.16 Participants with systolic blood pressure >120 mm Hg or diastolic blood pressure >80 mm Hg who are unwilling to start antihypertensives (see [Section 5.4](#) for recommendations for management of hypertension during the study), or participants with systolic blood pressure > 140 mm Hg, or diastolic blood pressure > 90 mm Hg, with or without use of antihypertensive medication (participants *may not* enroll onto the study until blood pressure (BP) is \leq 140/90 mm Hg with or without antihypertensive medication).
- ___ 3.2.17 Participants with a recent history (< 6 months) of a major bleed which will be defined as a symptomatic bleeding in a critical area or organ, such as intracranial, intraspinal, intraocular, retroperitoneal, intraarticular or pericardial, or intramuscular with compartment syndrome, and/or bleeding causing a fall in hemoglobin level 2 grams/dL or more or leading to transfusion of two or more units of whole blood or packed red cells.
- ___ 3.2.18 Participants on any dose of warfarin or on full dose anticoagulation with other agents (including low molecular weight heparin, antithrombin agents, antiplatelet agents and full dose aspirin) within 7 days prior to study enrollment; participants on prophylactic doses of low molecular weight heparin and low-dose anticoagulants are allowed.
- ___ 3.2.19 Cardiac related illnesses including, but not limited to:

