5.4 Dose Modifications for Hypertension

Hypertension: this is an expected AE within the class of anti-neoplastic drugs affecting the VEGF pathway. In participants with a baseline BP $\geq 120/80$ mm Hg and cardiac risk factors (history of hyperlipidemia, smoking, diabetes, treatment for hypertension, African-American ethnicity),⁶⁷ hypertension should be anticipated and therefore may need more aggressive management *prior to* first dose of study drug. In these cases, it is recommended that an internal medicine specialist or cardiologist be consulted to assist in management of hypertension. BPs are required at all visits prior to drug administration. All BP measurements should be made after the patient has been in a sitting or supine position for 5 minutes or longer.

Unless the patient has congestive heart failure, significant peripheral edema and/or significant salt intake that is difficult to modify, ACE inhibitors, ARBs and calcium channel blockers (nifedipine and amlodipine) may be more effective than diuretics.⁶⁸

Grade 2 Hypertension (systolic BP 140 - 159 mm Hg or diastolic BP 90 - 99 mm Hg)

Participants with grade 2 hypertension as documented by two or more different measurements - that are at least 30 minutes apart and measured by a healthcare provider - must be initiated on antihypertensive therapy per the treating physician. Treatment with sEphB4-HSA may continue during this time. BP should be rechecked 3-5 days after initiation of an antihypertensive, or after approximately 5 half-lives to allow antihypertensive drug levels to achieve steady state (~5 days for an antihypertensive dosed daily and ~3 days for one dosed twice daily). If systolic blood pressure (SBP) is still ≥ 140 mm Hg and/or diastolic blood pressure (DBP) is ≥ 90 mm Hg, physician should increase the dose of the antihypertensive or add additional antihypertensive therapy as indicated. Continue to monitor BP and titrate antihypertensives every 3-5 days until target BP (<140/90 mm Hg) is achieved.

Grade 3 Hypertension (systolic BP ≥ 160 mm Hg or diastolic BP ≥ 100 mm Hg)

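### On its literal wording, the Section 4.5 removal criterion for hypertension needs both pressures raised, so sustained Grade 2 hypertension in one pressure on medication falls outside the only specific removal rule

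*Combined protocol and SAP*

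**What the plan says.** Section 4.5 lists the grounds on which participants are removed from study treatment and also brings in the criteria of Section 5.0. Its hypertension bullet reads: "Uncontrolled sustained hypertension, which will be defined as systolic BP > 140, and diastolic BP > 90, even with use of antihypertensive medications".

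Elsewhere, limits on the two pressures are joined differently:

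- **Entry (3.2.16).** The protocol excludes anyone with "systolic blood pressure > 140 mm Hg, or diastolic blood pressure > 90 mm Hg, with or without use of antihypertensive medication".
- **Grading (5.4).** The two definitions begin "Grade 2 Hypertension (systolic BP 140 - 159 mm Hg or diastolic BP 90 - 99 mm Hg" and "Grade 3 Hypertension (systolic BP ≥ 160 mm Hg or diastolic BP ≥ 100 mm Hg".
- **Recheck on antihypertensives (5.4, Grade 2).** Therapy is increased "If systolic blood pressure (SBP) is still ≥ 140 mm Hg and/or diastolic blood pressure (DBP) is ≥ 90 mm Hg". The target is below 140/90.

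The dosing consequences differ by grade:

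- **Grade 2.** Section 5.4 says "Treatment with sEphB4-HSA may continue during this time" and directs titration every 3 to 5 days until the target is reached. Its text gives no time limit, hold, dose reduction or stop.
- **Grade 3.** Section 5.4 says "treatment with sEphB4-HSA must be held until hypertension returns to target BP (<140/90 mm Hg", and a four-week hold for hypertension ends treatment.
- **Section 5.2.** Its rule for symptomatic Grade 2 toxicity ends in stopping, but its heading reads "Dose Modifications for Non-Hematologic Toxicity (EXCEPT hypertension", so it does not apply here.

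Section 4.5 also has general grounds, namely unacceptable adverse events and investigator judgment that further treatment is no longer acceptable. Section 5.4 refers to a Hypertension Management Schema, a figure whose content was not in the text available for this review.

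**The concern.** Hypertension is an expected toxicity of this drug. It set the phase I maximum tolerated dose (Section 2.3.8: two of six participants at 20 mg/kg every 14 days), and hypertension rates were part of the reason for moving to 10 mg/kg. A mandatory removal rule for uncontrolled pressure should therefore give the same answer at every site.

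With *and* in the definition, the rule orders cases oddly. A participant at 141/91 on medication must come off treatment, while one at 155/85 on medication need not. That second participant would have been barred from entry by 3.2.16 and is still off target under 5.4. What is at stake is continued dosing, for up to 12 cycles, of someone in whom titration has failed on one pressure, with removal left to individual judgment. The primary analysis is not at stake.

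**Working it through.** The plan states no figure on this point. The check is to put example readings through each rule as worded.

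| Sustained reading on medication | 4.5: systolic > 140 and diastolic > 90 | 3.2.16: systolic > 140 or diastolic > 90 | 5.4 off target: systolic ≥ 140 and/or diastolic ≥ 90 | 5.4 grade |
|---|---|---|---|---|
| 141/91 | met | met | yes | 2 |
| 159/90 | not met (90 is not > 90) | met | yes | 2 |
| 155/85 | not met | met | yes | 2 |
| 135/98 | not met | met | yes | 2 |
| 165/85 | not met | met | yes | 3 |
| 138/102 | not met | met | yes | 3 |

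Section 5.4 allows three Grade 2 patterns: systolic only, diastolic only, or both. Section 4.5 reaches only the third, and not all of that, because 159/90 has both pressures in the Grade 2 range of 5.4 and still fails the strict inequality on diastolic.

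**Does another specific rule catch isolated Grade 2?**

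1. The four-week stop in 5.4 needs a hold. Grade 2 alone does not cause one.
2. The limit of 28 days on dose delay (4.5 and 5.6) needs a delay. Grade 2 hypertension does not require one.
3. The Grade 2 stop in 5.2 excludes hypertension.
4. The general grounds in 4.5 can be used, but each depends on judgment.

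**Is Grade 3 affected?** No. Readings of 165/85 and 138/102 fail the 4.5 wording, but 5.4 holds the drug for both. The hold also covers partial recovery: a participant titrated from 165/95 to 155/85 is still not below 140/90, so stays on hold and is discontinued at four weeks. The gap is therefore Grade 2 without a Grade 3 hold. The text of 5.4 does not address someone who recovers fully, resumes, and later settles in isolated Grade 2; the point does not rely on that case.

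**Effect of changing the connective.** With *or* and the same cut-offs, the removal limit becomes the 3.2.16 column, so all four Grade 2 examples meet it once titration has failed.

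**Effect on the design.** Grade 2 hypertension is not among the unacceptable toxicities in 10.1. The 10.2 figures depend on n = 20, the limits of 9 responders and 3 toxicities, and the assumed rates. Exact binomial values are:

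- P(at least 9 responders given 0.30) = 0.113.
- P(at most 3 toxicities given 0.30) = 0.107.
- Power, taking response and toxicity as independent, is 0.943 × 0.867 = 0.818.

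These agree with the stated 0.11 and 0.82, and the removal criterion does not enter them.

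**The case against.** The strongest reply is that the sections do different jobs. Section 3.2.16 governs entry and 5.4 governs grading and titration, whereas 4.5 ends treatment. A protocol may titrate on either pressure and ask for more before removal, and 5.4 expressly allows dosing during Grade 2. It is true that neither 3.2.16 nor 5.4 is itself a removal rule for Grade 2, so a reader who infers a flat contradiction goes too far. A deliberately higher bar does not explain the result, however. Section 4.5 already mandates removal at 141/91, which is mild Grade 2, and exempts 155/85. No rationale is given for that order.

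Other replies carry some weight:

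- **Loose drafting.** *And* may have been meant as *and/or*. Nothing in 4.5 says so, and 5.4 writes *and/or* where it means it. If that was the intent, the correction is uncontroversial.
- **Edge effect.** The pair 141/91 and 159/90 turns partly on a boundary. The pair 155/85 and 135/98 does not.
- **Schema.** The figure in 5.4 could state what happens to uncontrolled Grade 2. This stands as a limit on the point.
- **No dose reduction first.** Recurrent Grade 3 is allowed a hold and a one-level reduction, while the fix removes isolated Grade 2 without a reduction. That asymmetry already exists for 141/91, so the fix extends it but does not create it.

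A reader might also infer that isolated hypertension of any grade goes unmanaged, or that such participants cannot be removed. The documents support neither: 5.4 covers Grade 3, and the general grounds in 4.5 remain open.

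**Conclusion.** The point holds in a narrow form, at minor severity. By its wording, the specific removal criterion misses sustained Grade 2 hypertension on medication unless both pressures exceed their cut-offs. This matters for participants who have not had a Grade 3 hold, for whom the visible text leaves removal to discretion.

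The conclusion rests on two assumptions: that *and* in 4.5 is read as written, and that the 5.4 schema adds no rule for this case. The size in participants is unknown, because the documents give no rate of persistent isolated Grade 2 hypertension on medication.

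A stronger reading would be that the removal cut-off should also move from > to ≥ to match 5.4. The inconsistency does not require this. Section 3.2.16 uses > as 4.5 does, and the change would be a separate tightening that could bring in, for example, someone held at 140/80.

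**What to change.** Amend the one bullet in 4.5, changing the connective and keeping the cut-offs:

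*Uncontrolled sustained hypertension, defined as systolic BP > 140 mm Hg or diastolic BP > 90 mm Hg that persists despite titration of antihypertensive medications under Section 5.4.*

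Check this wording against the 5.4 schema. How long to titrate before calling the hypertension uncontrolled is the sponsor's clinical choice. Entry at exactly 140/90, which 3.2.16 permits, does not meet this criterion.

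The cost is one bullet in an amendment, with no change to sample size, visits or the 10.2 decision rule. The downside is that a few more participants could meet the removal criterion.
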